- 4) Conduct sub-group analyses to explore any moderators on the association between potential determinants and fat use e.g. sex, diet status (e.g. High CHO Vs Low CHO dietary intake), menstrual cycle (females only) and sex hormone thresholds.

Study Design:

This study proposed is an observational, exploratory cross-sectional study that plans to recruit a total of 200 male and female adults aged between 18 – 65 years, who are classed as either ‘healthy’ or ‘at-risk of metabolic disease’. Participants will visit a laboratory at the University of Bath on four occasions. All visits will take place at a Department for Health Laboratory on the University of Bath Main Campus. Please see figures 1 and 2 for a study outline and schematic, respectively.

Following advertisement of the study, interested participants will be asked to contact the Chief Investigator ([name] [CI]) for further information via email/telephone correspondence. If after reading the information sheet, the potential participant is still interested in partaking, they will be invited to attend a preliminary meeting at the University of Bath Main Campus to further discuss the trial (Visit 1).

Visit 1 (approx. 45 minutes)

After the potential prospective participant has read the information sheet, seen the study flowchart / schematic outlining the protocol and study demands, had any questions answered and are able to competently describe back the study to the CI, they will be asked to sign two consent forms (one copy for them, one copy for the CI) if they are still interested in partaking. Study eligibility and health screening (via questionnaires) will then be assessed and if eligible, a short familiarisation process will take place and a demographic and lifestyle questionnaire completed. The familiarisation process involves breathing through a mouthpiece for 5 minutes

and 10 minutes of very low intensity cycling (at 30, 40 and 65-Watts). This is in an attempt to increase the accuracy of data obtained on each main trial day (Visit 2 and 3). Dates will then be scheduled for Visit 2, 3 and 4 and the collection of the preliminary main trial day lifestyle measurements (diet and physical activity monitoring). For female participants who are eumenorrheic or oligomenorrheic and not using contraception (i.e. combined pill, intrauterine device), Visit 2 and 3 will be scheduled to be completed in the same stage of the menstrual cycle via the self-reported menstrual cycle questionnaire.

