Once the FAT_{MAX} test is finished, the main trial day is complete. If this is the first main trial day (Visit 2), participants will then complete the above protocol 7-28 days later. Participants will be asked to maintain their habitual lifestyle between Visit 2 and 3.

Visit 4 (approx. 50 minutes)

Visit 4 will take place between 2 – 7 days after Visit 3. Participants will be asked to arrive to the laboratory after a 12-hr fast at a similar time of the day to visit 2 and 3 (\pm 1 hr), at least 48-hrs after Visit 3 and having consumed 568 mL of plain water upon waking. Additionally, the participant will be asked to avoid any vigorous physical activity and alcohol consumption for the prior 24 hrs to the beginning of this Visit. After voiding, a dual energy X-ray absorptiometry (DEXA) scan will be performed to assess body composition. After the scan, the **OPTIONAL** skeletal muscle and / or fat biopsy will then be taken (see below for the skeletal muscle and adipose tissue sampling techniques). Once this visit is finished, the participant's involvement in the study is complete. I

Study Participants:

We plan to recruit a total of 200 male and female adults who are 'healthy' or 'at risk of developing metabolic disease'. Participants will be recruited from within the University of Bath and the surrounding areas by email, online and social media platforms (Twitter, University of Bath webpage and callforparticipants.com), poster advertising and word of mouth.

The inclusion criteria is:

- Male or Female
- Aged between 18 – 65 years

- No current or previous history of known cardio-pulmonary, metabolic or musculoskeletal disease
- A body mass index (body mass in kilograms divided by height in metres squared) between 18.9 and 35 kg/m².
- All physical activity / fitness levels
- Willingness and sufficiently able to meet the study demands (including the preliminary main trial day measurements and procedures, and maintain their habitual lifestyle (physical activity and diet) across the main study period [Visit 1 to Visit 4]).

Exclusion criteria:

- Taking any medication that may influence study parameters (lipid and / or carbohydrate metabolism)
- Any reported use of substances, other condition, or behaviour deemed either to pose undue personal risk to the participant, or introduce bias into the experiment.
- Any bleeding disorder or taking any medication which impacts blood coagulation
- Any female who is breast-feeding or may be / is pregnant

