- Individuals with radio-opaque implants (such as a knee or other joint replacement) or medical devices (such as a pacemaker)

Additional exclusion criteria for individuals who opt in for the optional skeletal muscle and / or adipose tissue biopsy are:

- Known tendency towards keloid scarring
- Known sensitivity or allergy to any local anaesthetic medicines

Study Methodology:

Questionnaires

Participants will complete several questionnaires throughout the study as outlined under 'Study Design' (please see the enclosed documents outlining each questionnaire). These consist of:

- a) Health History questionnaire (completed by all participants)
- b) Physical activity readiness questionnaire (PAR-Q; completed by all participants)
- c) Lidocaine Administration Health Questionnaire (to be completed by participants who opt for the muscle and / or adipose tissue biopsy)

- d) Participant Questionnaire (Age, sex, ethnicity, smoking status, dietary patterns / special dietary requirements; completed by all participants)
- e) Self-reported Menstrual Cycle / Reproductive Status (Females only)
- f) Long Form International Physical Activity Questionnaire (IPAQ; [69])

Diet Assessment

In an attempt to standardise upon commencement of trials and analyse potential associations with study parameters, participants' energy and macronutrient intakes will be assessed via a self-weighed diet diary in the 7 days prior to Visit 2 and 3. This must include at least 3 weekdays, at least 1 weekend day and the immediate 48-hrs prior to visit 2. Participants will be asked to replicate their diet for 48-hrs prior to each main trial day (i.e. Visit 2 and 3). For Visit 4 participants will be asked to record their evening. Participants will be provided with a set of digital weighing scales (Pro Pocket Scale TOP2KG, Smart Weigh Scales) to accurately weigh food and energy-containing drink products. Diet records will be analysed to estimate energy and macronutrient intakes (Nutritics Ltd., Dublin, Ireland). These diaries will additionally be used to assess study / standardisation compliance.

Physical Activity / Energy Expenditure Assessment

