Two x 10 mL whole blood samples will be collected from a vein in the antecubital fossa via venepuncture (BD Vacutainer Safety Lok, BD, USA) into a 10 mL syringe (BD Plastipak, BD, Madrid, Spain) by qualified and experienced phlebotomists (primarily [name] & [name]). The blood sample on each main trial day will be split equally into a 5 mL ethylenediaminetetraacetic acid-coated tube (K3 EDTA, Sarstedt, Germany) and a 10 mL serum/clotting activator tube (Serum Z/10 ml, Sarstedt, Germany). The EDTA tube will be centrifuged immediately, while the serum tube will be left to stand at room temperature for 20-min before being centrifuged, both for 15 min at 1700 g (3,000 rpm) and at 4°C (Heraeus

Biofuge Primo R, Kendro Laboratory Products Plc., UK). Plasma and serum samples will be extracted from the EDTA-treated and non-treated tubes, respectively, by splitting equally across eight Eppendorf tubes (4 x plasma, 4 x serum) and immediately frozen at -20°C , before longer-term storage at -80°C for later batch analysis. These samples will be analysed for the analysis of metabolites and hormones associated with substrate metabolism (e.g. glucose, non-esterified fatty acids, triacylglycerol, adrenaline, estrogen).

The buffy coat layer (consisting of white blood cells) will also be isolated by removing and discarding any remaining plasma in the EDTA-treated tube and then carefully pipetting the buffy coat layer into an Eppendorf. The buffy coat layer will be immediately frozen at -20°C , before longer-term storage at -80°C for later genotyping analysis of single nucleotide polymorphisms (SNP's). SNP's previously shown to be associated with BMI, waist-circumference and adipose tissue distribution will be analysed for similar relationships and also with substrate metabolism (e.g. FTO [fat mass and obesity associated gene], FFAR1 [long chain fatty acid G-coupled protein receptor]).

Skeletal Muscle Biopsy Procedure (Optional)

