A sample size estimation of 200 participants was determined via two methods. Firstly, R² values (36% and 13%) from two stepwise multiple linear regression models predicting the variance of peak fat use during exercise (g/min and mg/kg Fat Free Mass/min, respectively) in 300 healthy male and female adults were used [54]. Using these R² values, 42 and 119 participants were required, respectively, to provide a 95% chance of detecting this variation in PFO with α set at 0.05. Secondly, Cohen [76] defines the above effect sizes as large and

medium, respectively. A sample size estimation chart produced by Miles and Shevlin [77] with ten predictors was consulted as a guide. Conservatively, to detect a medium effect size with a power of >95%, approximately 180-190 participants would be required. Taking into account the above, a sample of two-hundred participants was decided upon to account for rolling recruitment, loss of follow-up data due to study withdrawal, non-completers, replacement of drop-outs and any unforeseen issues in data collection.

To minimise the negative impact of loss of follow-up data to validity, participants will be provided with a detailed participant information sheet and have the experimental protocol explained verbally before the onset of the study. They will be advised to carefully consider the required time investment and effort required to complete the study. As such, we hope that exclusions based on likely withdrawals can be accounted for prior to participation. Any unforeseen change in circumstance or withdrawal of consent resulting in loss of follow-up data will be fully documented in the final trial report.

Statistical / Data Analysis

Primary Outcome Measure:	Maximal rate of whole-body fat oxidation (mg/kg FFM/min)
Secondary Outcome Measures:	Maximal rate of whole-body fat oxidation (g/min)
	FAT _{MAX} (% of maximum oxygen consumption)
	FAT _{MAX} (% of Watt max)
	FAT _{MAX} (% of Heart Rate max)
	Resting rate of whole-body fat oxidation (mg/kg FFM/min)
	Resting rate of whole-body fat oxidation (g/min)
	Resting Metabolic Rate (kcal/min)
	$\dot{V}O_{2peak}$
	Habitual Energy Intake (kcal/day)
	Habitual Macronutrient Intake (grams per day)
	Habitual Physical Activity Energy Expenditure (kcal/day)

	Menstrual Cycle (Self-reported and sex hormone concentrations in blood [Estrogen and Progesterone])
	Fasting measures of blood metabolites: Glucose, Triglycerides, Cholesterol, NEFA, glycerol

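### Cycle-stage matching leaves out women with an intrauterine device who still cycle, and the hormone analyses do not separate users of hormonal contraception

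*Combined protocol and SAP*

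**What the plan says.** **Scheduling.** Study Design, Visit 1, asks for Visits 2 and 3 to fall at a common cycle stage, judged from self-report, for a restricted group: "For female participants who are eumenorrheic or oligomenorrheic and not using contraception (i.e. combined pill, intrauterine device". The Visit 2 and 3 section sets the gap between the two tests at 7 to 28 days (the background text says 7 to 14).

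**Analysis.** In Statistical / Data Analysis, item 2 correlates fat use with every variable and carries the significant ones into a hierarchical regression. Item 3 compares Visit 2 with Visit 3 by paired t-test, correlation, intraclass correlation, coefficient of variation, limits of agreement and typical error. Item 4 describes between-person variation after allowing for within-person variation. Objective 4 adds sub-groups that include "menstrual cycle (females only) and sex hormone thresholds", but no analysis item gives a method for them.

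**Hormone data.** The outcome table lists "Menstrual Cycle (Self-reported and sex hormone concentrations in blood [Estrogen and Progesterone". The blood-sample section counts estrogen among the "metabolites and hormones associated with substrate metabolism (e.g. glucose, non-esterified fatty acids, triacylglycerol, adrenaline, estrogen".

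**Eligibility.** The exclusion criteria include "Taking any medication that may influence study parameters (lipid and / or carbohydrate metabolism", "Any bleeding disorder or taking any medication which impacts blood coagulation" and "Individuals with radio-opaque implants (such as a knee or other joint replacement) or medical devices (such as a pacemaker". None of them mentions contraception.

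**The concern.** The matching rule has two conditions: the woman cycles, and she uses no contraception. The second removes women who meet the first. Matching exists to keep cycle stage out of the test-retest comparison, so the condition that matters is whether she cycles, not whether she uses a contraceptive.

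The repeat-visit data carry much of the study's argument. The background says that determinants can be identified more precisely only once within-person variability has been accounted for. Avoidable variation in the Visit 2 versus Visit 3 difference therefore affects Objective 3 directly, and Objective 2 through it.

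The sex-hormone analyses have a separate gap. If women on hormonal contraception enter the same correlations and threshold groups as women who cycle naturally, the same blood concentration may stand for different hormonal states, and nothing in the plan keeps them apart.

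Finally, a screener determines eligibility and schedules visits in the same Visit 1 session, using text that appears to expect pill and IUD users in one place and could be read to exclude them in another.

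**Working it through.** The plan gives no figure to reproduce here. The check sets the sections side by side, then uses a short piece of algebra for direction.

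**Step 1: who is matched.** Applying the Visit 1 rule as written:

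- Eumenorrheic or oligomenorrheic, no contraception: matched.
- Eumenorrheic or oligomenorrheic, IUD: not matched, because the IUD is a named example of contraception.
- Combined pill: not matched.

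The second line needs no outside fact: the protocol's own term describes a woman who cycles, and its own wording exempts her. The rule does not distinguish types of IUD, so the documents do not show how many IUD users this covers.

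**Step 2: what her data do to the reliability statistics.** Let σ² be the error variance of one test, p the share of participants who are unmatched but cycling, and τ² the variance of the stage effect on the Visit 2 minus Visit 3 difference. Assume that this effect averages zero and is independent of error. Then

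- variance of the difference = 2σ² + pτ²
- squared typical error = (2σ² + pτ²)/2 = σ²(1 + p·r/2), where r = τ²/σ².

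The typical error and limits of agreement widen and the intraclass correlation falls. If one pooled error figure is then used in item 4, it is also applied to men and to matched women, who did not contribute the extra variation.

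Neither p nor r is in the documents. As an illustration only, assume that half of the 200 participants are women, that 20–40% of those use a pill or IUD, and that half of these users have a non-hormonal device and still cycle. That gives 100 × 0.20 × 0.5 = 10 to 100 × 0.40 × 0.5 = 20 women, so p = 10/200 = 5% to 20/200 = 10%. The squared typical error then rises by a fraction 0.05r/2 = 0.025r to 0.10r/2 = 0.05r. With r unknown, this gives a direction and a scale, not an estimate.

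**Step 3: hormone analyses.** Item 2 applies to every variable, and the outcome table includes estradiol and progesterone. Neither item 2 nor Objective 4 names contraceptive status as a stratum, covariate or exclusion. As written, users of hormonal contraception would be included. That their measured values may differ in meaning from those of cycling women is a general premise, not something the documents state.

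**Step 4: eligibility.** An exemption for pill and IUD users is needed only if such women can enrol. The medication criterion turns on whether a drug *may* influence lipid or carbohydrate metabolism, and the protocol itself links estrogen to substrate metabolism, so a literal reader could apply it to a hormonal pill. The device criterion does not exempt an IUD. The sections can be read as conflicting, but the text does not compel that reading.

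**The case against.** The strongest reply is that the Visit 1 text is specific and the exclusions are general. A screener holding the whole protocol sees pill and IUD users provided for by name. The examples of excluded implants and devices are a joint replacement and a pacemaker, and medication use is a listed study variable, so the medication exclusion was evidently meant to be applied with judgement. This stands. A reader might infer that the exclusions remove many contraceptive users; the documents neither say so nor give any share of users. What remains is a request to make the wording explicit.

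Second, the data to deal with cycle stage may already be in hand. Blood is drawn at both main visits, estradiol and progesterone are measured, and women complete a reproductive-status questionnaire that is not reproduced in the document. The scheduling rule cannot be applied without asking about contraceptive use, so it must already be asked; only the recording of its type is unverified. This also stands, but measuring stage is not the same as adjusting for it, and no adjustment is specified.

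Third, natural stage variation could be called a genuine part of within-person variability. However, the protocol chose to remove it for other cycling women. Leaving it in for some mixes two quantities in one reliability estimate.

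**Conclusion.** The point holds in a limited form. On the protocol's own wording, a cycling IUD user is exempt from stage matching, and the effect is to add variation to the Visit 2 versus Visit 3 statistics and to the correction that relies on them. The absence of a contraceptive stratum in the sex-hormone analyses is a second, real gap.

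Three stronger readings are not supported. That all IUD users still cycle cannot be concluded, because device types are not separated. That the sex-hormone and menstrual analyses are confounded, or their threshold groups misclassified, is not shown: the plan is silent on contraceptive users rather than committed to a particular grouping, and low estradiol already has more than one explanation without them. That the eligibility criteria contradict each other outright depends on a literal reading of general wording.

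The size cannot be derived from the documents, which give no number of women, contraceptive users or device types and no stage effect on fat oxidation. Severity is low to modest: the study is observational and exploratory, its primary outcome (peak fat oxidation per kg of fat-free mass) is not defined by cycle status, and the hormone thresholds are one example among several sub-groups.

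**What to change.** 1. **Matching rule.** Base same-stage scheduling of Visits 2 and 3 on whether the woman is eumenorrheic or oligomenorrheic, whether or not she uses an IUD. The cost is slightly harder scheduling for cycling IUD users.
2. **Hormone and menstrual analyses.** Confirm that the reproductive-status questionnaire records contraceptive type. Pre-specify users of hormonal contraception as a separate reproductive-status category, stratified or analysed on their own, in the sex-hormone correlations and the Objective 4 sub-groups. The cost is one coded variable and fewer women in the endogenous-hormone analyses.
3. **Eligibility wording.** Reconcile the Visit 1 scheduling text with the medication and device exclusions by stating explicitly how hormonal contraception and IUDs are treated. Which eligibility rule applies is for the investigators to decide. The cost is a few sentences.

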Visit 2 and 3 (Main Trial Days; approx. 90 minutes)

Preliminary Main Trial Day Lifestyle Measurements:

For the 7-days prior to Visit 2 and at least 2-days prior to Visit 3, the participant will be instructed to:

- Wear a physical activity monitor (Actiheart™)
- Complete a self-weighed diet diary (this includes at least 3 week-days and at least 1 weekend day prior to Visit 2, and the immediate 48-hrs prior to the beginning of each main trial day)
- Record step count via a provided pedometer or personal device (e.g. mobile phone app)

This is to assess participant's physical activity levels, energy expenditure and energy / macronutrient intake. Participants will be asked to replicate their physical activity levels and diet 48-hrs prior to the beginning of each main trial day (Visit 2 and 3). Additionally, they will be asked to avoid any vigorous physical activity for the prior 48 hrs and avoid alcohol consumption for the prior 24 hrs to the beginning of each main trial day.

Main Trial Days:

Visits 2 and 3 are identical. For both of the main trial days, participants will be asked to arrive at the laboratory after fasting for 12 hrs (\pm 1 hr). The main trial days can take place either in the morning or afternoon, but must be at the same time of the day (\pm 1 hr) and must take place within 7-28 days of each other. The main trial days will follow the below protocol:

- i. Upon arrival to the laboratory, participants will be asked to provide an approximate 10 mL urine sample and void.
- ii. Anthropometric measurements (body stature (cm), weight (kg), and waist and hip circumference (cm)) will then be assessed.

- iii. After a brief period of rest in a semi-supine position in a resting laboratory, 4 x 5-min resting expired gas samples will then be collected into Douglas Bags to determine resting metabolic rate and substrate use at rest via indirect calorimetry. The International Physical Activity Questionnaire (IPAQ) will also be completed during the initial brief resting period.
- iv. A 10 mL blood sample will then be taken via venepuncture for analysis of metabolites and hormones involved in substrate metabolism, and genotyping.
- v. After the 10 mL blood sample, the maximal incremental graded cycling test to volitional exhaustion (FAT_{MAX} test) will be completed (see below for the protocol).

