Expired gas samples will be collected into 100 - 150 L Douglas bags (Cranlea & Hans Rudolph) via a mouthpiece connected to a two-way, T shaped non-rebreathing valve (Model 2700, Hans Rudolph Inc, Kansas City, Missouri). This valve is connected to a 3-way stopcock valve (Hans Rudolph Inc, Kansas City, Missouri) through falconia tubing (Cranlea). Expired gas samples will be analysed for concentrations of oxygen and carbon dioxide through paramagnetic and infrared transducers, respectively (Mini MP 5200, Servomex Group Ltd., Crowborough, East Sussex, UK). The sensors will be calibrated to a two-point low and high calibration (Low: 99.998% Nitrogen, 0% Oxygen and carbon dioxide; High: Balance nitrogen mix, 20.06% oxygen, 8.11% carbon dioxide) using certified, known concentrations (BOC Industrial Gases, Linde AG, Munich, Germany). The sensors will be turned on for 30 minutes prior to each trial. Ambient oxygen and carbon dioxide concentrations will also be noted during collection of expired gas samples to adjust for changes in these concentrations which may have occurred due to global climate change and laboratory contamination [71]. Expired gas samples will be analysed for at least two minutes and until values are stable. Volume and temperature of expired gas samples will be measured using a dry gas meter (Harvard Apparatus) and digital thermometer (HI98509 Checktemp® 1, Hanna Instruments Ltd, Bedfordshire, UK), respectively, during gas evacuation. Ambient temperature, humidity and barometric pressure will be recorded through a weather station (Technoline WS 6730, TechnoTrade Import-Export GmbH, Berlin, Germany).

Substrate use rates will be estimated at rest and during exercise through the stoichiometric equations outlined by Jeukendrup and Wallis [72] including adjustment for the contribution of glycogen metabolism during exercise.

Anthropometric Measurements and Body Composition Analysis (DEXA Scan)

The following anthropometric measurements will be taken: a) Body mass to the nearest 0.1 kg using electronic weighing scales (BC-543 Monitor, Tanita, Tokyo, Japan); b) Body stature to the nearest 0.1 cm using a wall mounted/attached stadiometer (Holtain Ltd, UK) with participants head positioned in the Frankfort plane and after inhalation of a deep breath [73]; c) Body mass index (BMI) calculated as mass in kilograms, divided by the square of participant's stature in metres (kg/m^2); d) Fat mass index calculated as fat mass in kilograms

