estimated by DEXA divided by height in metres squared; e) Waist and hip circumference (cm) to the nearest 0.1 cm using a measuring tape (SECA 201, Hamburg, Germany) with participants arms folded across their thorax. Waist circumference is measured at the narrowest point between the 10th Rib and top of the iliac crest at the end of a 'normal' expiration [73]. Hip circumference is measured at the point of greatest posterior protuberance of the buttocks [73]; f) Waist to hip ratio calculated by dividing waist circumference by hip circumference; and g) Body fat % to the nearest 0.1% through the bioelectrical impedance analysis function on the electronic weighing scales (BIA; BC-543 Monitor, Tanita, Tokyo, Japan). Anthropometric measurements will be determined while participants are barefoot and wearing light clothing.

A Dual Energy X-Ray Absorptiometry (DEXA) scan will be performed at Visit 4 (QDR, Discovery W, Hologic, UK). While DEXA was primarily designed to measure bone mineral density, a secondary application offered is a non-invasive, precise estimation of total and localized body composition. Prior to the scan, the device will be calibrated using a quality control material provided by the manufacturer. Participants will be scanned in light clothing (i.e. shorts for men and athletic clothing for women). Participants will be positioned centrally on the scanning bed; with feet spread apart and hands placed in a mid-prone position such that there was a gap between the arms and trunk. This allows regions of interest to be defined by an operator using the software provided by the manufacturer (QDR for Windows, Hologic, UK).

Urine sample analysis

The 10 mL urine sample will be collected into a 50 mL tube (Corning, Corning Inc, USA) and will be analysed for urine specific gravity by a hand-held refractometer (SUR-NE ATEGO, ATEGO Co Ltd, Tokyo, Japan).

Blood sample collection and separation / analysis

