	Fasting measures of Adipokines: Leptin, Adiponectin
	Fasting measures of Catecholamines: epinephrine and norepinephrine
	Fasting measures of sex hormones: 17 beta-estradiol, testosterone, progesterone
	Fasting pancreatic derived hormone concentrations: insulin and glucagon
	Hydration Status: Urine Specific Gravity
	Age (years)
	Sex
	Ethnicity
	Smoking Status
	Medication / Supplement Use
	Dietary Patterns / Requirements
	Body Fat Percentage
	Lean Body Mass (kg)
	Body Fat Distribution
	Waist and Hip Circumference
	Fat Mass Index
	Genotype analysis
	Skeletal Muscle Characteristics (Protein Content and / or Activity)
	Adipose Tissue Characteristics (Protein Content and / or Activity)

Data will be checked for normal distribution prior to analysis via Shapiro-Wilk's normality test and visual inspection of histograms. Parametric tests will be conducted on normally distributed data. Non-normally distributed data will be log-transformed if appropriate or the equivalent

non-parametric tests will be conducted. Statistical significance will be set at $P < 0.05$. The statistical analysis for the study objectives identified above are as follows:

- 1) The effect of body composition on whole-body fat use will be tested by separating groups into defined categories (e.g. lean, overweight or obese) and conducting a one-way ANOVA and mixed design model. The latter to test for any interaction effects across the two main trial days.
- 2) To identify determinants / characteristics that may be associated with whole-body fat use, correlation analysis will firstly be conducted between whole-body fat use at rest and during exercise with each variable. Statistically significant correlates will then be added to a follow-up hierarchical regression analysis to predict whole-body fat use at rest and during exercise.
- 3) At a group level, intra-individual variation in whole-body fat use will be tested by a paired sample t-test. A range of further reliability / variability tests will be conducted to comprehensively determine intra-individual variation: Pearson correlation coefficient, Intra Class Correlation, Coefficient of Variation, Bland-Altman plots with 95% Limits of Agreement and Typical Error. Additionally, individual data will be plotted on graphs alongside group means.

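### The only written derivation of body fat % is the weighing scales' impedance reading, although the Visit 4 DEXA scan could supply it

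*Combined protocol and SAP*

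**What the plan says.** The section Anthropometric Measurements and Body Composition Analysis (DEXA Scan) lists the body-size measures. Item g is "Body fat % to the nearest 0.1% through the bioelectrical impedance analysis function on the electronic weighing scales". No other derivation of body fat % appears in the document.

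Item d of the same list uses the other device: "Fat mass index calculated as fat mass in kilograms" "estimated by DEXA divided by height in metres squared". The paragraph after the list says of DEXA that "a secondary application offered is a non-invasive, precise estimation of total and localized body composition". It makes no comparable statement about impedance.

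Under Visit 4, "a dual energy X-ray absorptiometry (DEXA) scan will be performed to assess body composition". Only the biopsies at that visit are optional.

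The secondary outcomes under Statistical / Data Analysis include "Body Fat Percentage" with no instrument, and separately lean body mass, body fat distribution and fat mass index. For Objective 2, each variable is first correlated with fat use, and then "Statistically significant correlates will then be added to a follow-up hierarchical regression analysis".

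The schedule for Visits 2 and 3 says "Anthropometric measurements (body stature (cm), weight (kg), and waist and hip circumference (cm)) will then be assessed". It does not mention an impedance reading, so the visit that supplies item g is not stated either.

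**The concern.** Body fat % is a candidate determinant in Objective 2. A candidate enters the regression only if its single correlation is significant at P < 0.05. Random error in a candidate weakens that correlation, so it can lower the variable's estimated contribution or keep it out of the model.

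An analyst who follows the methods text would use the impedance value, because it is the only one defined. A scan that the protocol regards as precise will already be on file for everyone who attends Visit 4. The plan gives no reason for taking one total-adiposity variable from the scales and another, fat mass index, from the scan. Nor does it say which source applies if both are available, so the choice could be made after the results are seen.

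**Working it through.** **The plan's own figures.** No figure in the documents concerns impedance error, agreement with DEXA, or the spread of body fat %. The sample sizes of 42 and 119 can be reproduced from R² = 0.36 and 0.13 at 95% power with an overall F test, if 5 and 3 predictors are assumed (the plan does not state the counts). They do not depend on how body fat % is measured.

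**Link between the two variables.** If scan mass and scale mass agree, DEXA body fat % = 100 × fat mass index / BMI. The scan that yields item d therefore already yields a body fat %. An assumed 3-point difference between devices corresponds to 0.03 × 18.9 = 0.57 up to 0.03 × 35 = 1.05 kg/m² of fat mass index across the eligible BMI range.

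**Shrinkage of correlations.** Assumptions, none of them from the documents:
- DEXA is error-free.
- The impedance-DEXA difference is unrelated to DEXA body fat % and to fat use.
- The difference has SD *d* of 3 to 5 points, and DEXA body fat % has SD *s* of 8 to 10 points.

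Then r(impedance) = r(DEXA) × *s* / √(*s*² + *d*²).

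| *s* | *d* = 3 | *d* = 4 | *d* = 5 |
|---|---|---|---|
| 8 | 8/√73 = 0.936 | 8/√80 = 0.894 | 8/√89 = 0.848 |
| 10 | 10/√109 = 0.958 | 10/√116 = 0.928 | 10/√125 = 0.894 |

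The factor runs from 0.848 to 0.958, so correlations shrink by 4 to 15%. Variance explained by this variable alone falls by 1 − 0.958² = 8% to 1 − 0.848² = 28%.

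**Effect on the screen.** Power for one correlation, two-sided 0.05, with all 200 participants, is approximately Φ(atanh(r) × √197 − 1.96).

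| True r | No shrinkage | Factor 0.958 | Factor 0.848 |
|---|---|---|---|
| 0.20 | 81% | 78% | 67% |
| 0.30 | 99% | 99% | 95% |

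A weak association with body fat % becomes somewhat easier to miss. A moderate one is still found.

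**The case against.** The best defence is that item g says what the scales record, not what is analysed. The outcome list names no device, and the stated purpose of the Visit 4 scan is body composition, so the investigators may intend the DEXA value. This is partly right: the analysed source is not settled. But the only definition on the page is impedance, and under either reading the same sentence is missing.

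The second defence is that a total-adiposity measure from DEXA is already planned. Fat mass index goes through the same screen, as do lean mass and fat distribution. This stands. The shrinkage applies only to correlations that use impedance body fat %, and Objective 2 does not lose adiposity as a determinant.

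Three stronger readings are tempting, and the documents support none of them.
- A reader might infer that the plan contradicts itself. It does not: two devices, each labelled, can be recorded side by side.
- A reader might infer that the lean, overweight and obese groups of Objective 1 would be misclassified. The plan gives no body-fat cut-point, and its only numeric adiposity criterion is the BMI entry range of 18.9 to 35 kg/m². Any misclassification rate would describe an analysis that the plan does not specify.
- A reader might infer that the study repeats the problem raised in its introduction, where differing assessment of body composition is offered as a reason for inconsistent findings. That passage concerns differences between studies, not two measures on the same people.

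**Conclusion.** The point holds in a limited form. The one written derivation of body fat % uses the scales, while the protocol's own precise method is scheduled for everyone and already serves fat mass index. If the text is followed, correlations using body fat % would be about 4 to 15% too small. That range rests wholly on the assumed SDs, on DEXA being error-free, and on purely random disagreement between devices. An impedance error that varied with adiposity would break the last assumption, and the documents say nothing either way.

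Severity is minor. Body fat % is one of many secondary variables in an exploratory study, and neither the sample size nor the definition of the primary outcome depends on it.

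**What to change.** Add one sentence to the analysis section: body fat % in all analyses is DEXA fat mass divided by DEXA total mass, from the same Visit 4 scan as fat mass index. In item g, label the impedance value as descriptive only and name the visit at which it is taken.

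No new measurement is needed. The cost is that participants who miss Visit 4 have no analysed body fat %. If that loss matters, their impedance value can be used, flagged, in a sensitivity analysis.
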